2.2 Reducing Toxicity to Therapy

In head and neck cancer patients, compliance with combined modality treatment is essential to improve clinical outcomes. It is well known that compliance to treatment ranges from 50-70% and that the use of PEG tubes supports improved treatment compliance and outcomes by improving nutrient intake. Despite these findings, improved effectiveness has plateaued secondary to mucositis and side effects of multi-modal therapy including chronic fatigue, loss of muscle mass, and body fat. Various interventions have attempted to ameliorate the side effects of therapy in an effort to improve compliance. Medical therapies such as amifostine for radioprotection of normal tissue, and bezydamine, palifermin, and GCSF to reduce mucositis have not shown significant benefit.

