5. TREATMENT PLAN

This is a non-randomized, pilot Phase II clinical trial that will determine the safety of concentrated beet root given in conjunction with radiation or radiation plus chemotherapy for locally advanced head and neck cancer. This trial will enroll 25 subjects taking beetroot supplement with up to an additional 10 standard of care subjects that refuse participation in the beetroot supplementation but are willing to obtain strength outcomes during their cancer treatment for a maximum of 35 patients.

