5.1.4 Subjects will elect not to participate in beet root supplementation study

Subjects to elect not to participate in the beet root supplementation study will be asked to consider participation in an observational study of muscle strength testing that matches the muscle strength testing of those receiving beet root supplementation during their cancer treatment. These subjects will be performing cohort of non-therapeutic interventional subjects who will provide baseline information in a preliminary manner as a comparator to those subjects receiving beet root supplementation. This is not a randomization but rather utilization of subjects who would otherwise not be participating in the clinical trial. These subjects will be compensated for their time in a similar manner to subjects who are on the beet root supplementation study. A separate consent form will be used and a separate registration will be used for these patients.

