13.2 Sample Size/Accrual Rate

The primary endpoint of this study is treatment compliance, for the chemoradiation strata defined as completion of radiotherapy and 3 cycles of chemotherapy with no treatment delay with published historical rates average around 52.1% (30). For those receiving radiation alone, we predict higher compliance rates closer to 70% as these patients tend to experience less mucositis and adverse events during treatment. We anticipate 60% of patients will receive radiation alone versus 40% receiving chemoradiation. 25 total patients (10 – chemoradiation, 15 – radiation alone) receiving beet root supplementation, will result in 90% confidence intervals around each estimated compliance rate with a maximum widths of +/- 27.75% and 22.85% for chemoradiation and radiation alone respectively. The combined estimate of compliance will still have a 90% confidence interval estimate with a maximum width of +/- 17.7% as previously designed. For the 10 subjects in the observational cohort not receiving beet root supplementation, we will still be able to estimate compliance rates +/- 27.75% and obtain pilot data regarding strength outcomes during standard of care therapy. This design is not powered to compare compliance rates between treatment strata or beet root versus standard of care; instead it allows us to gain preliminary information about these rates with a certain amount of precision as pilot data for a larger, more definitive study. We plan to accrue patients over a 2 year period.

There will be a pre-specified safety consideration after half of the planned enrollment in the beet root supplementation (interim after 13) to verify acceptable treatment completion rates as compared to a published historical rate of 52.1%. Two prior beta distributions (non-informative and null-hypothesis based) will be considered with patient information collected from the first 13 enrolled in beet root arm to calculate the posterior probability that the mean proportion of successful completion is less than or equal to historical rates of 52.17% with corresponding 90% credible intervals. The study team will reconsider continuation of the protocol due to safety and feasibility concerns if either arm has a high probability of experiencing a success rate lower than published rates.

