13.3 Data Analysis

Following study completion, primary data analysis will include estimation of subjects achieving treatment compliance along with corresponding exact 90% binomial confidence intervals.

Other secondary endpoints listed in section 13.1 will be primarily descriptive as they are exploratory in nature; however means and standard deviations (or N and percentages where appropriate) will be estimated and summarized for each time point to gain more information of expected effect size differences between standard therapy and BR arms. Repeated measures ANOVA will be utilized to test for exploratory differences in these various measures over time points between BR and standard therapy arms. Kaplan-Meier curves will be presented for locoregional control and progression-free survival along with 90% confidence interval bounds. Exploratory log rank tests will be performed to assess for any preliminary differences in these survival outcomes by treatment arm.

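### Section 13.3 compares the beet root cohort with self-selected refusers without regard to chemotherapy stratum, so the exploratory effect sizes can mix beet root with chemotherapy

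*Combined protocol and SAP*

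**What the plan says.** Section 5 of the combined protocol and SAP forms the comparator from "up to an additional 10 standard of care subjects that refuse participation in the beetroot supplementation". Section 5.1.4 gives these patients a role "as a comparator to those subjects receiving beet root supplementation" and is open about how they arise: "This is not a randomization but rather utilization of subjects who would otherwise not be participating in the clinical trial".

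Section 13.3 sets the between-cohort analysis of the secondary measures: "Repeated measures ANOVA will be utilized to test for exploratory differences in these various measures over time points between BR and standard therapy arms". It also plans exploratory log-rank tests by arm for locoregional control and progression-free survival. No covariate, stratification or matching is named there or elsewhere. Section 13.3 says the summaries serve to learn what effect sizes to expect between the arms, and 13.2 describes the results as pilot data for a larger study.

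The plan treats chemotherapy as prognostic. Section 13.2 uses a historical compliance rate of 52.1% for chemoradiation, and for radiation alone it says "we predict higher compliance rates closer to 70% as these patients tend to experience less mucositis and adverse events during treatment". Section 5.1.1.3 says cisplatin makes mucositis and dysphagia worse. Section 13.2 splits the beet root cohort into 10 chemoradiation and 15 radiation-alone patients. The observational cohort gets no split and one pooled precision figure: "For the 10 subjects in the observational cohort not receiving beet root supplementation, we will still be able to estimate compliance rates +/- 27.75" percent.

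On feeding route, section 2.2 states that "the use of PEG tubes supports improved treatment compliance and outcomes by improving nutrient intake". Section 5.1 admits both PEG-fed and orally fed patients.

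**The concern.** The plan recognises two strata with different expected outcomes, uses them to size the beet root cohort, and then drops them when the cohorts are compared. Nothing makes the refusers' chemotherapy share match the planned 40% of the beet root cohort. If the share differs systematically, part of any difference in mucositis, strength, body composition or survival is due to chemotherapy.

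The repeated measures structure does not remove this. Baseline testing is before IMRT (5.1.5) and concurrent chemotherapy acts afterwards, so its effect lies in the change over time, which is what a cohort-by-time contrast measures.

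At stake is the effect size carried into a larger trial. The bias could make beet root look useful, or hide a real effect.

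**Working it through.** **1. The plan's precision figures.** The largest half-width of the exact (Clopper-Pearson) 90% interval, over all possible counts, is 27.76 points for n = 10, 22.81 for n = 15 and 17.67 for n = 25. Section 13.2 states 27.75, 22.85 and 17.7, so its figures reproduce to within 0.04 points.

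**2. Shift in compliance from case mix alone.** Inputs from 13.2: 52.1% for chemoradiation, 70% for radiation alone, and a 40% chemoradiation share in the beet root cohort. Assume no beet root effect.

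- Expected compliance at share f is 52.1f + 70(1 − f).
- Beet root cohort, f = 0.4: 0.4 × 52.1 + 0.6 × 70 = 62.84%.
- Apparent difference (beet root minus observational) = 17.9 × (f_obs − 0.4) points, or 1.79 points per 10-point gap in share.

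| Observational chemoradiation share | Expected compliance | Apparent difference |
|---|---|---|
| 0% | 70.0% | −7.2 |
| 20% | 66.4% | −3.6 |
| 40% | 62.8% | 0 |
| 60% | 59.3% | +3.6 |
| 80% | 55.7% | +7.2 |
| 100% | 52.1% | +10.7 |

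Within a stratum the difference is zero.

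**3. Error rate for a continuous secondary measure.** The documents give no chemotherapy effect on these measures. Assumption: the strata differ by 0.5 to 1 SD (within-stratum SD). Take a 40-point gap (40% in the beet root cohort, 80% in the observational cohort), n = 25 and 10, and no beet root effect. A two-sided 5% two-sample t-test stands in for the contrast in change from baseline. The bias is 0.4 × 0.5 = 0.2 SD to 0.4 × 1 = 0.4 SD. Simulation with 200,000 runs per setting gives these rejection rates:

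| Stratum difference | Mix fixed at 10/25 and 8/10 | Mix random at 40% and 80% |
|---|---|---|
| 0.5 SD | about 7% | about 8% |
| 1 SD | about 13% | about 15% |

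A normal approximation that sets the residual SD to 1 gives 8.3% and 18.8%. It is too high because, with no stratum term in the model, the spread between strata also sits in the residual.

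**4. Chance imbalance.** With both cohorts drawn from a 40% population, a share gap of 20 points or more occurs with probability 0.30. In the same simulation with both cohorts at 40%, the unadjusted test rejects about 5.0% of the time at either stratum difference. Chance imbalance is therefore already covered by the nominal error rate; only a systematic gap is not.

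**5. Precision cost of adjusting.** The unadjusted standard error is √(1/25 + 1/10) = 0.374 SD. With c of 10 comparators on chemoradiation, the stratified variance is 1/(1/v₁ + 1/v₂), where v₁ = 1/10 + 1/c and v₂ = 1/15 + 1/(10 − c). The standard error is 0.381 for c = 2, 0.374 for c = 4, 0.380 for c = 6 and 0.401 for c = 8.

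**The case against.** The strongest reply is that the limits are largely disclosed. Section 5.1.4 says the comparator is not randomised and its information preliminary. Section 13.2 disclaims power for comparing the strata or the cohorts, and 13.3 calls the secondary analyses descriptive and the tests exploratory. No decision hangs on them. Adjustment also cannot remove the effect of refusal itself, and in 10 patients it leaves small cells. All of this stands and limits the severity. But low power widens an interval; it does not justify an avoidable bias in a point estimate meant for planning.

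Four stronger readings are tempting and not supported:

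- **A false compliance finding of up to 11 points.** Section 13.3 plans only estimation of compliance, with no between-cohort test, and the whole −7.2 to +10.7 range lies inside the observational cohort's ±27.75 points.
- **Refusers known to differ in chemotherapy or swallowing.** The documents say nothing on why patients refuse, and the supplement can be given by mouth or by tube (5.1.3). The existence and direction of a systematic gap are unknown.
- **Small cohorts as such inflating error.** Step 4 shows that they do not.
- **PEG feeding as a cause of mucositis differences.** Section 2.2 ties PEG to compliance and nutrition; the mucositis link is stated for chemotherapy only.

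**Conclusion.** The point holds as an avoidable weakness in an exploratory analysis and should be corrected. The between-cohort methods in 13.3 omit a variable that the plan itself treats as prognostic, in a comparison formed by self-selection.

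The size is conditional on a systematic difference in chemotherapy share. On the plan's own rates it is 1.8 compliance points per 10-point gap, as description only. For continuous measures, a 40-point gap takes a nominal 5% test to about 7% to 15%; this rests on the assumed 0.5 to 1 SD stratum difference and on a t-test standing in for the repeated measures contrast. The documents give no figure from which to size the effect of PEG status.

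A reader might infer that adjusting for stratum would turn the contrast into an estimate of the beet root effect. It would not, because refusal remains confounded with cohort.

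**What to change.** In section 13.3:

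1. Add treatment stratum (radiation alone or chemoradiation, as initially prescribed) as a fixed effect, with its interaction with time, to the between-cohort repeated measures models.
2. Stratify the exploratory log-rank tests by the same variable.
3. Report observational-cohort compliance by stratum beside the matching beet root stratum.
4. Tabulate baseline chemotherapy and PEG status by cohort. Section 5.1.1.3 already asks for feeding-tube placement and use to be recorded. The observational calendar (10.3) has no diet row, unlike 10.2, so confirm that PEG status is captured there.
5. State that between-cohort differences remain subject to self-selection and are not estimates of a beet root effect.

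The cost is SAP wording, about one degree of freedom per model term, and small cells in the observational cohort. The loss of precision is slight: the standard error goes from 0.374 SD to at most 0.401 SD in the cases in step 5. With at most 10 comparators, further covariates are not practical, which is why PEG status is tabulated and not modelled.

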5.1.5 Testing procedures at Baseline, Midpoint and Endpoint of therapy

All testing procedures, unless otherwise indicated, will be performed at the Markey Cancer Center (MCC) and the Center for Clinical and Translational Science (CCTS). Testing will occur at Baseline (Pre-IMRT), Midpoint (week number 7-8 following IMRT initiation), and Endpoint (4-6 weeks following Midpoint testing). A range of testing times at midpoint and endpoint are provided for subject convenience and flexibility with medical follow-up appointments. Primary outcome measure: 1) IMRT treatment compliance- No delays in treatment of radiation and/or chemotherapy (Cycles: Namely 35 fraction of daily radiation therapy (Monday-Friday) with 100 mg/m² cisplatin on days 1, 21, & 43. Total duration of therapy = 50 days). Treatment compliance will be defined as completion of all radiotherapy or completion of all radiotherapy plus prescribed chemotherapy without dose reduction or delay of radiation therapy that would extend treatment beyond 50 days.; Secondary outcome measures: 1) muscle strength/function, 2) serum/salivary nitrate/nitrite, 3) preservation of fat-free mass (CT/DXA), 4) mucositis symptoms, 5) nutrition assessment, 6) quality of life g. Details of each test are provided in section 9.0.

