5.3 Duration of Therapy

Subjects will be removed from study if one of the following occurs:

- Subjects who do not complete at least 50% of the planned medical therapy
- Intercurrent illness that prevents further administration of medical treatment,
- Unacceptable adverse event(s),
- Patient decides to withdraw from the study, or
- General or specific changes in the patient's condition render the patient unacceptable for further treatment in the judgment of the investigator.

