13.4.2 Evaluation of Outcomes

All patients included in the study will be assessed for treatment compliance, even if there are major protocol treatment deviations or if they are ineligible. All of the patients who met the eligibility criteria (with the possible exception of those who received no study medication) will be included in the intent to treat analysis for the primary completion endpoint as well as all secondary outcomes.

Due to concerns of potential non-compliance of taking all beet supplements over the course of primary treatment, a per protocol analysis will also be performed for all patients that consume at least 3 servings of the required beet supplements per week. Percentage of beet supplements taken will also be reported as part of this subgroup analysis.

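### Section 13.3 names repeated measures ANOVA with no rule for missed visits; in its classical form it would not deliver the intent-to-treat set promised for secondary outcomes

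*Combined protocol and SAP*

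**What the plan says.** Section 5.1.5 sets three test occasions: "Testing will occur at Baseline (Pre-IMRT), Midpoint (week number 7-8 following IMRT initiation), and Endpoint (4-6 weeks following Midpoint testing". Section 5 plans 25 patients on beetroot and up to 10 who decline it but agree to testing.

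For the measures taken at these visits, section 13.3 names one inferential method: "Repeated measures ANOVA will be utilized to test for exploratory differences in these various measures over time points between BR and standard therapy arms". It gives no model form, covariance structure, estimation method or rule for a missed visit, and no other section does. The same section says "Other secondary endpoints listed in section 13.1 will be primarily descriptive as they are exploratory in nature", and that "means and standard deviations (or N and percentages where appropriate) will be estimated and summarized for each time point". The stated purpose is to learn about expected effect sizes. Section 13.2 describes the results as pilot information for a larger study.

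On the analysis set, section 13.4.2 says that eligible patients, possibly excepting those who took no study medication, "will be included in the intent to treat analysis for the primary completion endpoint as well as all secondary outcomes".

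Section 5.3 lists who is taken off study. The list begins with "Subjects who do not complete at least 50% of the planned medical therapy" and goes on to intercurrent illness, unacceptable adverse events and withdrawal.

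**The concern.** Classical repeated measures ANOVA needs a complete row for each patient. Anyone without the midpoint or the endpoint leaves the analysis altogether, including the visits that were observed. That does not fit an intent-to-treat set for all secondary outcomes.

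Missed visits related to illness are foreseeable. The removal rules in section 5.3 act on patients who tolerate treatment badly, and section 5.1.1.3 expects severe mucositis or dysphagia in about two thirds of patients. Midpoint testing falls at the end of radiotherapy and asks for knee-extensor and handgrip effort, DXA and CT. If the patients who decline most are the ones who do not come, a completers-only analysis makes the average decline look smaller than it is. Two things are then at stake: the use of scarce data, and the changes over time that would be carried into the design of the next trial.

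**Working it through.** **1. The plan's own figures.** The plan gives no figure for this analysis. Its only design figures are the 90% confidence interval half-widths for compliance in section 13.2. The largest exact binomial half-widths are 27.76% (n = 10), 22.81% (n = 15) and 17.67% (n = 25), against the stated 27.75%, 22.85% and 17.7%. They reproduce, and they concern the primary endpoint only.

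**2. Patients left for a three-visit analysis.** Inputs: N = 25 and N = 10 (sections 5 and 13.2), and an assumed loss d at each of the two post-baseline visits, independent between visits. Expected completers = N(1 - d)².

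| d (assumed) | of 25 | of 10 |
|---|---|---|
| 5% | 22.6 | 9.0 |
| 10% | 20.2 | 8.1 |
| 20% | 25 × 0.64 = 16.0 | 10 × 0.64 = 6.4 |
| 30% | 12.2 | 4.9 |

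If only the endpoint is missed, the count is N(1 - d): 20 and 8 at 20%.

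**3. Change within a cohort, when missingness depends on the observed midpoint change.** All inputs are assumed: SD 1 at each visit, correlation 0.7 between visits, true changes from baseline of -0.60 SD (midpoint) and -0.40 SD (endpoint), and 25% missing at the endpoint. The log-odds of a missing endpoint rise by b for each SD of the measure by which the midpoint change is worse, with the intercept set to hold 25% missing. Large-sample simulation gives:

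| b | Completers: midpoint | Completers: endpoint | All observed visits: endpoint |
|---|---|---|---|
| 0 | -0.60 | -0.40 | -0.40 |
| 0.5 | -0.53 | -0.37 | -0.40 |
| 2 | -0.38 | -0.29 | -0.40 |

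The midpoint is fully observed here, so an analysis of all observed visits returns -0.60 for it. The scale of b matters a little. The SD of the change is √(2 × (1 - 0.7)) = 0.77; with b from 0.5 to 2 per SD of change, the completers' midpoint estimate runs from -0.51 to -0.35.

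**4. The same, when missingness depends on the unseen endpoint.** With the inputs of step 3 and b from 1 to 2 per SD of the measure, the all-visits estimate of the endpoint change is -0.30 to -0.24 against a true -0.40. A second set of assumptions (true changes -0.50 and -0.40, 20% missing, b = 1 per SD of change) gives -0.43 and -0.27 for completers and -0.50 and -0.30 for all observed visits. Using all visits restores the midpoint but only part of the endpoint.

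**5. Difference between cohorts.** The planned test compares cohorts, so the bias in the difference is the bias in one minus the bias in the other. From step 3, the midpoint bias is -0.53 + 0.60 = +0.07 under weak dependence and -0.38 + 0.60 = +0.22 under strong dependence. Strong in the beetroot cohort and weak in the observational cohort gives +0.22 - 0.07 = +0.15 SD in favour of beetroot. The reverse gives -0.15. Equal dependence gives 0.

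**6. Treatment modality.** If baseline is one of the responses, a modality main effect m adds the same amount at every visit. The change is then (visit effect + m) - (baseline effect + m), and m cancels. Only modality by visit can alter the cohort-by-visit contrasts.

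**The case against.** The strongest reply is that the plan nowhere limits the analysis to patients with all three visits. A reader might infer that it does. The documents do not support that: it is a property of the classical method, and the same name is also used for mixed-model fits that keep partial data. The intent-to-treat sentence says who belongs to the set, not how a missing outcome is treated. This stands, and it makes the conflict conditional. It does not remove the point, because the plan names a method whose classical form fails its own analysis set and says nothing to exclude that form.

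Second, effect-size information will come largely from the per-visit means and SDs, which are not limited to completers. In step 3 the planned midpoint summary would already show -0.60. This stands. The restriction affects the ANOVA, not those summaries.

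Third, the bias figures describe loss within a cohort and rest on assumed inputs, while the test is between cohorts. This also stands. A reader might infer that the comparison is tilted for or against beetroot in a known direction; step 5 shows that either sign is possible.

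Fourth, the analyses are exploratory. That limits the consequences, but the pilot exists to inform a larger study, so sound estimates of change are part of what it is meant to produce.

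**Conclusion.** The point holds in conditional form. Section 13.3 leaves both the model and the missing-visit rule open. Read as classical repeated measures ANOVA, it would analyse fewer patients than section 13.4.2 promises: about 16 of 25 and 6 of 10 at an assumed 20% loss per post-baseline visit, with a range of about 23 and 9 (5% loss) to 12 and 5 (30% loss). If missingness follows decline, the average loss within a cohort is understated, illustratively -0.53 to -0.38 SD at midpoint against -0.60. If missingness is unrelated to change, there is no bias, only lost data. No dropout rate, SD or correlation is given in the documents, so these sizes are illustrations.

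The primary compliance endpoint is not touched. A reader might also infer that a mixed model cures the problem; it does so only where missingness depends on values that were observed. Nor do the documents support a weekly mucositis comparison between cohorts as part of the remedy: the calendar in section 10.3 schedules mucositis for the observational cohort at three visits only, and section 11.1 says that cohort is not followed for toxicity.

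**What to change.** In section 13.3, for the continuous measures, replace repeated measures ANOVA with a linear mixed model for repeated measures:

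- REML, unstructured covariance and small-sample degrees of freedom, using all observed visits.
- Baseline as one of the responses, so that patients with only a baseline visit stay in the analysis; no separate baseline covariate.
- Terms for cohort, visit and cohort by visit. If the sponsor wishes to adjust for radiation alone or chemoradiation, include modality by visit, since a main effect alone leaves the change contrasts essentially unchanged.
- Estimates with 90% confidence intervals.
- A table of missing visits by cohort and visit, with reasons, and a simple sensitivity analysis for missingness not at random.

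The cost is a short change to the statistical section and routine programming, with no new data. The downside is reliance on missing at random, which the sensitivity analysis is there to probe. If a mixed model was intended all along, the same wording settles it.

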5.1.3 Beetroot Administration

Study Supplements:

Subjects will be given 10 grams of concentrated organic beetroot crystals to mix with 120ml of water (BEETELITETM). Beetelite study supplement readily dissolve in water and may be given via gastrostomy tube or orally.

Daily Supplement Administration:

Subjects will begin daily supplementation following baseline measures (1-2 weeks before 7-week IMRT and for a minimum of 4 days) and will continue supplementation 4-6 weeks after treatment. Patients will be taught to self-administer their assigned study beverage by mouth and via PEG (as needed) by study staff during the baseline measurement period for the entirety of the trial. Patients requiring enteral support will be taught how to self-administer their assigned study beverage by a CRA or CRN. Compliance will be monitored by verbal assessment at clinic visits and by collection of written logs. Written instructions (Appendices E and F) for proper mixing of study beverage powders with water will be provided to both study volunteers and MCC staff involved in supplement administration and supervision. MCC staff will supervise the initial self-administration to ensure uniformity of ingestion. Subjects will be required to record the supplement intake in a dietary log which will be reviewed frequently at clinic visits.

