- CRNs serving as study personnel may offer observation or administration assistance if patient requests this and may document supplement compliance.
- Patients will be instructed to make up any missed doses by taking up to 1 additional dose per day on the weekend days. Patients will receive 5 doses per week (for M-F) and will be instructed to never exceed 1 dose per day.

4-6 weeks post-IMRT (discharge period):

- After completion of IMRT the participant will be instructed to continue daily (M-F) self-administration (PO or PEG) until completion of endpoint measures.
- For patients requiring supplement administration assistance at discharge, a family member or caregiver will be identified and taught to provide assistance.
- On the day of discharge and during scheduled follow-up visits, the CRA will distribute the pre-measured supplement packets needed for daily administration.
- Participants will continue to follow the supplement mixing protocol and be reminded to consume their assigned supplement within 30-minutes of mixing.
- Supplement compliance will continue to be encouraged by weekly phone calls by study personnel and compliance logs/supplement counts will occur at least twice per month.

Supplementation on Testing Days

On testing days, The BEETELITE™ solution (beet root) will be administered on-campus 20-45 minutes before subjects undergo the baseline, midpoint (following IMRT), and endpoint (4-6 weeks following midpoint) strength/endurance measures. Prior to testing, subjects will not have to refrain from standard oral care, using antibacterial mouth wash, or chewing gum 48 hours before testing sessions because the BEETELITE™ product does not rely on salivation/oral bacteria to convert dietary nitrate to nitrite (23). Previous studies have administered up to 500mL of beet root per day with nitrate concentrations of 5.5 mMol (24), 6.2mMol (7, 25), 5.2mMol (26), and 5.1mMol (27). Plasma nitrite (NO_2^-) levels in these aforementioned studies also increased following dietary nitrate supplementation.

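### Section 13.3 does not say which term of the repeated measures ANOVA compares the cohorts, and neither candidate gives a baseline-referenced effect size

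*Combined protocol and SAP*

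**What the plan says.** Section 13.3 gives one sentence on testing the secondary measures between cohorts: "Repeated measures ANOVA will be utilized to test for exploratory differences in these various measures over time points between BR and standard therapy arms". It names no model term, baseline covariate, change score or significance level. The same section says these endpoints "will be primarily descriptive as they are exploratory in nature", and that means and standard deviations "will be estimated and summarized for each time point to gain more information of expected effect size differences between standard therapy and BR arms".

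The visits are set in section 5.1.5: "Testing will occur at Baseline (Pre-IMRT), Midpoint (week number 7-8 following IMRT initiation), and Endpoint (4-6 weeks following Midpoint testing". The calendars in 10.2 and 10.3 schedule strength, DXA, CT, quality of life and nitrate/nitrite at all three visits in both cohorts.

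Section 5 gives the cohort sizes: "This trial will enroll 25 subjects taking beetroot supplement with up to an additional 10 standard of care subjects that refuse participation". Section 5.1.4 describes how the comparator arises: "This is not a randomization but rather utilization of subjects who would otherwise not be participating in the clinical trial".

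The position of the first supplement dose matters here. Section 5.1.3 says "Subjects will begin daily supplementation following baseline measures", but later in the same section the supplement "will be administered on-campus 20-45 minutes before subjects undergo the baseline, midpoint (following IMRT), and endpoint" strength and endurance measures. Section 5.1.7 places CT, quality of life and DXA before the testing-day dose, and plasma, saliva and strength testing after it.

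**The concern.** Baseline comes before radiotherapy and before the course of daily supplementation, so it cannot show an effect of either. A repeated measures ANOVA over the three visits nevertheless treats it as an outcome level. The consequence depends on which term is read, and the plan leaves that open until the data are in hand.

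The comparator consists of patients who declined the supplement, so a starting difference in strength or body composition is a real possibility. One of the two readings would report such a difference as a beetroot effect. The other would not, but it returns an F statistic rather than the effect-size information that 13.3 wants. The study is meant to supply pilot data for a larger one (13.2), and it has at most 10 comparators. A contrast that can be carried forward with an interval is therefore worth having.

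**Working it through.** **The plan's own figures.** Nothing is stated for this analysis. The only precision figures in 13.2 concern compliance: ±27.75%, ±22.85% and ±17.7% at n = 10, 15 and 25. The maximum half-widths of exact 90% binomial intervals are 27.76%, 22.81% and 17.67%, so those figures reproduce. They do not bear on the ANOVA.

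**Inputs from the documents.** 25 and 10 patients; three visits; no randomization.

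**Assumptions, not in the documents.** SD 1 at each visit; equal correlation ρ between visits (0.5, 0.7 or 0.8); effect d = 0 at baseline and the same at midpoint and endpoint; a starting gap b that is constant over visits; no dropout; two-sided 5%.

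**What each analysis estimates.**

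- Arm main effect: [b + (b + d) + (b + d)]/3 = (2/3)d + b
- Change of the midpoint/endpoint mean from baseline: (d + b) − b = d
- The same mean with baseline as covariate (ANCOVA): (d + b) − ρb = d + b(1 − ρ)
- Arm-by-time: zero for any constant b when d = 0, but a 2-df test of any pattern, with no single estimate

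For the main effect, d = 1 and b = 0 gives 0.67. With d = 0 and b = 0.5 it gives 0.50. With d = 1 and b = −0.67 it gives about zero, so a 1 SD effect is hidden.

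**Standard errors.** With 1/25 + 1/10 = 0.14:

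- Main effect: √[0.14(1 + 2ρ)/3] = 0.306, 0.335, 0.348 at ρ = 0.5, 0.7, 0.8
- Change: √[0.14 × 1.5(1 − ρ)] = 0.324, 0.251, 0.205
- ANCOVA: √[0.14(1 − ρ)(1 + 2ρ)/2] = 0.265, 0.224, 0.191
- Arm-by-time noncentrality: (25 × 10/35) × (2/3)(0.5²)/(1 − ρ) = 2.38, 3.97, 5.95 on (2, 66) df

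**Simulated power for d = 0.5 SD, b = 0.**

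| Analysis | ρ = 0.5 | ρ = 0.7 | ρ = 0.8 |
|---|---|---|---|
| Arm main effect | 18% | 17% | 16% |
| Arm-by-time, 2 df | 26% | 39% | 56% |
| Change, midpoint/endpoint mean | 33% | 48% | 66% |
| ANCOVA, midpoint/endpoint mean | 44% | 56% | 71% |

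**Simulated rejection rate for d = 0, b = 0.5 SD.**

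| Analysis | ρ = 0.5 | ρ = 0.7 | ρ = 0.8 |
|---|---|---|---|
| Arm main effect | 36% | 30% | 29% |
| Arm-by-time, 2 df | about 5% | about 5% | about 5% |
| Change, midpoint/endpoint mean | about 5% | about 5% | about 5% |
| ANCOVA, midpoint/endpoint mean | 14% | 9% | 8% |

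The ANCOVA rates reflect the remaining bias b(1 − ρ) = 0.25, 0.15 and 0.10 SD.

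**Is baseline pre-dose?** In the 5.1.7 order it is for CT, quality of life and DXA. For strength/endurance and nitrate/nitrite in the beetroot cohort it is not, by 5.1.7 and the testing-day text of 5.1.3. The statement in 5.1.3 that daily dosing follows baseline measures points the other way. Where baseline follows a dose, both a change score and a covariate would also remove part of any acute effect.

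**The case against.** The strongest reply is that the sentence in 13.3, which speaks of differences over time points between arms, naturally means arm-by-time. That test works on within-patient error, so it already removes stable between-patient spread and is not biased by a constant gap. This stands. A reader might infer from the sentence that the planned result is necessarily diluted and carries the starting difference, or that it throws away most of the available precision. The documents support neither inference, because they never name the arm main effect as the test.

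The precision argument also needs care. At a single visit with ρ = 0.8, the 90% half-width for the cohort difference is 0.63 SD unadjusted, 0.40 SD for change and 0.38 SD for ANCOVA; at ρ = 0.7 the last two are 0.49 and 0.45 SD. Against a change contrast, covariate adjustment narrows the interval only modestly. Single-visit ANCOVA has 32%/44%/58% power at ρ = 0.5/0.7/0.8, only 6, 5 and 2 points above the 2-df test. The clear gain comes from the 1-df contrast on the midpoint/endpoint mean.

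Nor does covariate adjustment cure selection. It keeps b(1 − ρ) of a stable gap, which the change score does not. It should therefore not simply replace the planned test.

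Finally, the comparison is exploratory, and the visit-by-visit means and SDs will show baseline by cohort whatever test is run. That limits the stakes. It does not settle which term will be read, and it does not supply an interval for the effect.

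**Conclusion.** The point holds as one of specification and efficiency. The plan leaves open two readings that behave very differently. Under the main effect, a third of the effect is lost and the whole of a stable starting gap is reported as an arm difference; a 0.5 SD gap with no true effect is declared significant in about 29% to 36% of trials. Under arm-by-time there is no such bias, but there is no effect size either, and power is 7 to 10 points below the change contrast and 15 to 18 points below ANCOVA on the midpoint/endpoint mean.

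These sizes rest on assumed correlations, an assumed 0.5 SD effect that is equal at both later visits, an assumed constant gap, and full follow-up of 25 and 10 patients. If the effect differed between midpoint and endpoint, the averaged contrast would lose some of its advantage. The algebra for the main effect does not depend on ρ. The primary compliance estimate and its intervals are untouched.

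**What to change.** For continuous measures, replace the repeated measures sentence in 13.3 with:

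> The cohort difference in the mean of midpoint and endpoint relative to baseline, and at each visit, will be estimated with a 90% confidence interval, both as change from baseline and with baseline as a covariate. The arm main effect of an ANOVA that includes baseline will not be used. Baseline values will be shown by cohort, and the comparison will be labelled non-randomized and exploratory.

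Apply the covariate version where baseline is measured before any supplement: CT, quality of life and DXA in the 5.1.7 order. Section 5.1.7 lets CT be rescheduled within 7 days of the other measures, so the actual order should be checked for any scan that was moved. For strength/endurance and nitrate/nitrite, the two statements in 5.1.3 and the order in 5.1.7 must first be reconciled, and the SAP should then say whether baseline for those measures is pre-dose or post-dose.

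The cost is a few lines of SAP text and slightly more analysis, with no new data. Two estimates per measure will sometimes disagree. With a stable starting gap the expected disagreement is b(1 − ρ), and reporting both estimates makes it visible.
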